4.4 Definition of Dose-Limiting Toxicity (DLT)

A Dose-limiting Toxicity (DLT) is defined as follows:

- Allergic reaction requiring medical intervention
- Acute bronchospasm requiring medical intervention
- Other acute AEs of interest requiring immediate medical intervention

Allergic reactions and acute bronchospasm not requiring intervention (Grade 1) are usually considered subject-specific and are not included in the definition of DLT. In this protocol,

allergic reactions and acute bronchospasm not requiring medical intervention are not included in the DLT definition since such reactions may not be product and dose-specific with QR-010.

4.5 Determination of Maximum Tolerated Dose (MTD)

The MTD is defined as one dose level below the dose level at which 2 subjects receiving QR-010 experience a dose limiting toxicity (DLT) for dose cohorts 1-4 or within the first 4 weeks for dose cohorts 5-8. Dose escalation will occur based on the number of DLTs encountered according to the rules in Table 3, as assessed by the DSMC. Dose escalation will continue until the MTD is reached or the maximum dose included in the study, whichever is lower. With the highest planned fill dose of 50 mg, subject exposure will be approximately < 40 mg (< 80% efficiency of the eFlow including residual volume). For the MTD determination, the fill dose will be used.

Table 3: Dose Escalation Rules

| Number of Subjects Receiving QR-010 With a DLT at a Given Dose | Dose-Escalation Decision Rule |
|-----------------------------------------------------------------------|-------------------------------------------------------------------------------------------------------------------------------------------------------------------------------------------------------------------------------------------------------------------------------------------------------------------------------------------------------------------------------------------------------------------------------------------------------------------------------------------------------------------|
| 0 of 6 | Proceed to next dose level |
| 1 of 6 | If one serious AE (SAE) or Grade \geq 2 AE occurs, four additional subjects will be enrolled at the same dose. If no additional subjects experience a similar SAE or Grade \geq 2 AE in the same organ class, the dose escalation may continue pending review of safety by the DSMC. If \geq 2 subjects experience similar SAE or Grade \geq 2 AE of the same organ class, dose escalation is to be stopped, pending review by the DSMC. The preceding dose may be considered the MTD by the DSMC. |
| \geq 2 of 6 | Dose escalation will be stopped. The preceding dose will be considered the MTD. |

DLT = dose-limiting toxicity; MTD = maximum tolerated dose (one dose level lower than the dose level at which 2 or more subjects experience a DLT of the same organ class)

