4.3 Dose Escalation

The single dose escalation scheme will test fill doses of 6.25 mg to 50 mg over 4 dose levels, and the multiple dose escalation scheme will test fill doses of 6.25 mg to 50 mg given thrice weekly (tiw) for 4 weeks ([Table 1](#)). As described in Section 2.2.1, the dose delivered to subjects via the eFlow device is < 80% of the fill dose, hence the delivered doses that correspond to the dose escalation schemes are shown in [Table 1](#).

Table 1: Dose Escalation

| Dose Cohort | Fill Dose (mg) | Estimated Exposure Dose < 80% of Fill Dose (mg) |
|-----------------------------------------------------------------|----------------|----------------------------------------------------|
| Single Dose Cohorts | | |
| 1 | 6.25 | 5 |
| 2 | 12.5 | 10 |
| 3 | 25 | 20 |
| 4 | 50 | 40 |
| Multiple Dose Cohorts (administered tiw for 4 Weeks) | | |
| 5 | 6.25 | 5 |
| 6 | 12.5 | 10 |
| 7 | 25 | 20 |
| 8 | 50 | 40 |

tiw = thrice weekly (three times per week)

Dose escalation will initially proceed in single subject cohorts from fill dose level 1 (6.25 mg) to fill dose level 4 (50 mg).

Initiation of MAD Cohort 5 will be based on the safety profile of SAD Cohort 2. Initiation of Cohort 6 will be based on the safety profiles of Cohorts 3 and 5. Similarly, initiation of Cohort 7 will be based on the safety profiles of Cohorts 4 and 6, and finally, the initiation of Cohort 8 will be based on the safety profile of Cohort 7. The first dose between subjects in each cohort must be separated by a minimum of 4 hours.

For the single dose cohorts 1 to 4, dose escalation to the next cohort may occur upon recommendation of the DSMC after the subjects have been observed for at least 7 days and no DLTs have occurred or, if a DLT has occurred, per the dose escalation rules in Section 4.5. For the multiple dose cohorts 5 to 8, dose escalation to the next cohort may occur upon recommendation of the DSMC after the subjects have been observed for at least 7 days after the last dose (End of Treatment Visit). If a DLT occurs in any cohort, the AEs and DLTs will be reviewed by the Investigator and the DSMC before dosing can continue in that cohort. In addition, if ≥ 2 subjects experience a decrease in absolute FEV₁ of $\geq 15\%$ from baseline in any cohort, the data will be reviewed by the DSMC before dose escalation can continue.

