5.5 Study Completion and Discontinuation Criteria

5.5.1 Study Completion/Withdrawal

A subject will have the right to withdraw from the study at any time for any reason.

A subject will be discontinued from the study by the Investigator if unacceptable toxicity or withdrawal of consent occurs.

Subjects participating in a MAD cohort that is determined to be greater than the MTD based on dose escalation rules can opt to continue in the study at the next lower dose cohort (ie, at the MTD).

Subjects withdrawn from SAD cohorts should have all assessments conducted at the End of Study Visit at the time of withdrawal. Subjects withdrawn from MAD cohorts should have all

assessments conducted at the End of Treatment Visit as well as the End of Study Visit, for safety monitoring purposes.

Subjects who have completed a SAD cohort are eligible to participate in a MAD cohort, provided there is at least 90 days between the dose in the SAD cohort and the first dose in the MAD cohort.

Allergic reactions may include local dermatitis, angioedema, throat constriction, or anaphylaxis. Appropriate treatment may include administration of antihistamines, hydrocortisone, or epinephrine at the discretion of the assessing physician. Subjects diagnosed with a systemic allergic reaction requiring therapy will be withdrawn from the study.

Given the proposed mechanism of action of QR-010, it could be anticipated that subjects could experience a change in baseline cough, change in sputum quality, or change in sputum volume. A pulmonary exacerbation should be considered if these symptoms are accompanied by fever, body weight loss, generalized malaise. If a pulmonary exacerbation is diagnosed, appropriate interventions including appropriate additional antibiotics should be prescribed by the Investigator or treating physician. Subjects diagnosed with a pulmonary exacerbation requiring the addition of antibiotics will be withdrawn from the study.

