## 2. STUDY DESIGN

### 2.1. Synopsis of Study Design

This is a randomized, double-blind (investigator and subject), placebo-controlled, single ascending and multiple ascending dose-escalation study to evaluate the safety, tolerability and pharmacokinetics and pharmacodynamics of QR-010 in subjects with CF who are homozygous for the  $\Delta F508$  mutation. Immunogenicity is to be evaluated amongst other safety considerations. Exploratory clinical efficacy measures are also included. There are two parts to the Phase 1b study: the study will start with four single ascending dose (SAD) cohorts and will move through four multiple ascending dose (MAD) cohorts.

[figure not shown]
SAD (Cohorts 1-4): single dose inhaled administration. The doses for SAD cohorts are Placebo (0 mg), QR-010 6.25, 12.5, 25, or 50 mg. Subjects will receive the dose will be observed for a total 4 days, and will be discharged on Day 4. Subjects will return for PK and safety follow-up as an outpatient on Day 8.

MAD (Cohorts 5-8): multiple dose inhaled administration. The doses for the MAD cohorts are Placebo (0 mg), QR-010 6.25, 12.5, 25, or 50 mg, thrice weekly for 4 weeks, for a total of 12 doses per subject. Subjects are followed weekly with end of treatment (EoT) visit to be performed 7 days after last dose and a safety follow-up visit to be performed 28 days after last dose.

An independent Data Safety Monitoring Committee (DSMC) was designated to review all safety data at the end of each cohort and to determine the maximum tolerated dose (MTD).

A schematic of the study design is presented in Figure 1.

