## 2.3. Determination of Maximum Tolerated Dose (MTD)

The MTD is defined as one dose level below the dose level at which 2 or more subjects receiving QR-010 experience a dose limiting toxicity (DLT) in the same organ class for dose cohorts 1-4 or within the first 4 weeks for dose cohorts 5-8. Dose escalation will occur based on the number of DLTs encountered according to the rules in Table 3, as assessed by the DSMC. Dose escalation will continue until the MTD is reached or the maximum dose included in the study, whichever is lower. With the highest planned fill dose of 50 mg, subject exposure will be approximately < 40 mg (< 80% efficiency of the eFlow including residual volume). For the MTD determination, the fill dose will be used.

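### The MTD has two incompatible definitions inside both the protocol and the SAP: any two DLTs, or two DLTs in the same organ class

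*Protocol*

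**What the plan says.** Wordings that set the MTD on any two DLTs:

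- Protocol 4.5, text: "one dose level below the dose level at which 2 subjects receiving QR-010 experience a dose limiting toxicity (DLT".
- Protocol Table 3 and SAP Table 2, row for two or more of six QR-010 subjects with a DLT: "Dose escalation will be stopped. The preceding dose will be considered the MTD". The row is the same in both documents and carries no organ-class condition.

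Wordings that require the same organ class:

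- Footnotes to protocol Table 3 and SAP Table 2: "one dose level lower than the dose level at which 2 or more subjects experience a DLT of the same organ class".
- SAP 2.3, text: "2 or more subjects receiving QR-010 experience a dose limiting toxicity (DLT) in the same organ class".

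The row for one of six uses organ class for a different purpose. It adds four subjects and says that, if none of them has a similar event "in the same organ class, the dose escalation may continue pending review of safety by the DSMC".

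On roles, SAP 2.1 says the DSMC is "to review all safety data at the end of each cohort and to determine the maximum tolerated dose (MTD". Protocol 4.3 adds, for the cohort concerned: "If a DLT occurs in any cohort, the AEs and DLTs will be reviewed by the Investigator and the DSMC before dosing can continue". SAP 2.5.1 sends the reader to the protocol and the DSMC charter for the criteria. SAP section 5 declares no change from the protocol.

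**The concern.** A table row and the footnote beneath it give different definitions of the same quantity, and this happens in both documents. The SAP text sides with the footnote and the protocol text with the row.

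The disputed case can arise. Protocol 4.4 counts as DLTs allergic reactions, acute bronchospasm and other acute AEs of interest that need intervention. The AE-of-interest list in protocol Table 2 includes hypotension and liver test elevation beside the respiratory events. One bronchospasm and one hypotension at the same dose gives an MTD at the preceding dose on one wording and no MTD on the other.

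Identifying the MTD is part of the primary objective (protocol 3.1). It may also matter during the trial, because protocol 5.5.1 says: "Subjects participating in a MAD cohort that is determined to be greater than the MTD based on dose escalation rules can opt to continue" at the next lower dose. Whether that option opens may depend on which definition is applied.

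**Working it through.** The documents give no operating characteristic for the MTD rule, so there is no stated figure to reproduce. The contradiction itself rests on the text alone. The arithmetic below shows only how often it would matter.

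**Inputs.** Six QR-010 subjects per cohort (protocol 13.2). The following are assumptions: a DLT probability p per subject, at most one DLT per subject, and two organ classes with shares s₁ and s₂, split 80/20 or 50/50. Six of the eight events in protocol Table 2 are respiratory, which makes a dominant class plausible, but that counts list entries and not event frequencies.

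**Given exactly two DLTs.** P(different classes) = 2·s₁·s₂, which is 2 × 0.8 × 0.2 = 0.32, or 2 × 0.5 × 0.5 = 0.50. With four equal classes it is 1 − 4 × 0.25² = 0.75.

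**Over all six-subject cohorts.** With two classes the rules disagree only when exactly two DLTs occur, one in each class. Writing p₁ = p·s₁ and p₂ = p·s₂:

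P(disagree) = 15 × 2·p₁·p₂·(1 − p)⁴ = 30·p₁·p₂·(1 − p)⁴

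- p = 0.10, 80/20: 30 × 0.08 × 0.02 × 0.6561 = 0.0315
- p = 0.10, 50/50: 30 × 0.05 × 0.05 × 0.6561 = 0.0492
- p = 0.20, 80/20: 30 × 0.16 × 0.04 × 0.4096 = 0.0786
- p = 0.20, 50/50: 30 × 0.10 × 0.10 × 0.4096 = 0.1229

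Any-class stopping is P(two or more of six) = 1 − (1 − p)⁶ − 6p(1 − p)⁵. Same-class stopping is that figure less P(disagree).

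| DLT rate | Any class | Same class, 80/20 | Same class, 50/50 | Gap (points) |
|---|---|---|---|---|
| 10% | 11.4% | 8.3% | 6.5% | 3.1–4.9 |
| 20% | 34.5% | 26.6% | 22.2% | 7.9–12.3 |
| 30% | 58.0% | 47.6% | 41.8% | 10.4–16.2 |

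At a 5% rate the gap is 1.0–1.5 points. More classes widen it: with four equal classes, same-class stopping falls to 3.5% at a 10% rate and 12.8% at 20%.

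**If expansion subjects count.** Assume that expansion follows exactly one DLT in six and that three of the four added subjects are active. The 3:1 ratio comes from protocol 13.3.1, but the documents do not state the split for added subjects.

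Any class: P(two or more of six) + P(one of six) × [1 − (1 − p)³]

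- p = 0.10: 0.1143 + 0.3543 × 0.2710 = 0.2103
- p = 0.20: 0.3446 + 0.3932 × 0.4880 = 0.5365

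Same class: when the first DLT is in class j, the added subjects produce no matching pair if none has a class-j DLT and at most one has a DLT in the other class. The second term is therefore P(one of six) × Σ sⱼ·[1 − (1 − p)³ − 3p(1 − sⱼ)(1 − p)²].

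- p = 0.10, 80/20: 0.0828 + 0.3543 × (0.8 × 0.2224 + 0.2 × 0.0766) = 0.1513
- p = 0.10, 50/50: 0.0651 + 0.3543 × 0.1495 = 0.1181
- p = 0.20, 80/20: 0.2660 + 0.3932 × (0.8 × 0.4112 + 0.2 × 0.1808) = 0.4096
- p = 0.20, 50/50: 0.2218 + 0.3932 × 0.2960 = 0.3382

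The gap is then 5.9–9.2 points at a 10% rate (21.0% against 15.1–11.8%) and 12.7–19.8 points at 20% (53.7% against 41.0–33.8%).

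**The case against.** The best case on the other side is that the operative rule is clear enough. The footnotes are abbreviation keys. The row for two or more of six is unconditional and identical in both documents, and the protocol 4.5 text agrees with it. The DSMC reviews every DLT and determines the MTD, and SAP 1.1 refers to version 4.0 of its charter, which may settle the point. The step-down in 5.5.1 is tied to the dose escalation rules, which is the title of the table holding that row. The primary endpoints in protocol 4.1.1 (AE incidence and severity, and DLT occurrence) do not depend on the MTD wording. All DLTs are summarised and listed, so either reading can be recovered afterwards.

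Much of this stands, and it limits the consequence. It does not remove the conflict. SAP 2.3 is body text and not an abbreviation key. SAP 2.5.1 refers back to a protocol that is itself split. The charter is not among the documents reviewed. DLT adjudication decides whether an event is a DLT, not how DLTs are combined into an MTD.

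A fair further objection is that same-class may be the intended concept. Protocol 5.5.2 stops treatment in a cohort when SAEs or Grade ≥2 AEs fall in the same system organ class in two or more subjects. The documents do not show which rule was meant, so the default proposed below is a recommendation and not a correction of a proven slip.

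A reader might also infer that escalation could continue past two DLTs of different classes. The row in both documents stops it. Nor is there an open gap after expansion: protocol 4.3 clears a dose only if no added subject has any Grade ≥2 AE of interest. Allergic reaction is a DLT that is missing from that list, but the 4.5 text still counts it and 4.3 still sends every DLT to the DSMC.

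**Conclusion.** The point holds as a wording conflict that should be fixed. Each document contains both definitions, and they disagree exactly when two or more QR-010 subjects have DLTs and no two share an organ class. In that case the declared MTD differs, and eligibility for the 5.5.1 step-down may differ.

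Under the assumed two-class splits, the case arises in about 1–5% of six-subject cohorts at DLT rates of 5–10% and about 8–16% at 20–30%. The documents support no particular rate or split, and protocol 2.2.1 calls the dosing scheme highly conservative, so the higher rates are illustration only.

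It would be too strong to say that the SAP replaced the protocol's rule, because the protocol's own footnote already carries the same-class condition. It would also be too strong to call this a subject-safety failure, because the stop and the DSMC review are in place on either definition.

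**What to change.** State one rule in protocol 4.5, protocol Table 3 and its footnote, SAP 2.3, and SAP Table 2 and its footnote, and say whether expansion subjects count.

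- **Default:** two or more QR-010 subjects with a DLT of any class at a dose level means that escalation stops and the MTD is the preceding dose. Delete the same-class condition from both footnotes and from SAP 2.3.
- **Alternative:** if the sponsor intends the same-class rule, write it into the protocol 4.5 text and the row for two or more of six in both tables.
- **Checks:** confirm that protocol 5.5.2 and the DSMC charter are consistent with the chosen rule.
- **Optional:** align the clearance condition in the row for one of six with protocol 4.3, and add allergic reaction to protocol Table 2. SAP 4.10.1.2.9 already treats it as an AE of special interest.
- **Clerical:** SAP 2.3 should point to SAP Table 2, not Table 3.

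The cost is wording changes and a charter check, with no new procedures. The price of the any-class rule over the same-class rule is more frequent stopping, by the gaps worked out above. Those gaps are larger if expansion subjects count, so that choice should be made knowingly.

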5.0 SELECTION OF STUDY POPULATION

5.1 Study Population

Subjects with a diagnosis of CF, homozygous for the $\Delta F508$ CFTR mutation who meet all inclusion and exclusion criteria will be eligible for participation in this study.

5.2 Selection of Subjects

Screening of subjects will be performed within 14 days prior to dosing. Medical history, physical examination and vital signs will be recorded. Subjects will undergo electrocardiogram (ECG), chest Xray (CXR), spirometry, and clinical laboratory safety testing. During the study subjects will be permitted to continue on their chronic medications that are considered standard of care for CF. For subjects using inhaled anti-infective agents, preferably the same therapy and dose should be administered throughout the study period (Refer to Section 6.3.1). Subjects with signs of a pulmonary exacerbation or other acute illness will not be included.

The exact number of subjects needed to complete the study depends on the number of cohorts required to reach the MTD and the number enrolled in each dose-escalation cohort. The number of subjects for each of the single dose and multiple dose escalation cohorts is 8 subjects, for a total of 64 subjects, but could theoretically expand to approximately 96 subjects if there are DLTs that require every dose cohort to be expanded. Subjects will be enrolled at approximately 20 study sites in North America and select European countries.

5.3 Inclusion Criteria

1. Able and willing to comply with the protocol and provide written informed consent prior to study-specific screening procedures
2. Able and willing to adequately and consistently perform spirometry as required by the protocol
3. Able and willing to participate in standardized airway clearance techniques
4. Confirmed diagnosis of CF as defined by iontophoretic pilocarpine sweat chloride test (sweat chloride) of > 60 mmol/L
5. Confirmation of cystic fibrosis transmembrane conductance regulator (CFTR) gene mutations homozygous for the $\Delta F508$ mutation. Genetic testing performed prior to the year 2000 must be re-confirmed.
6. Male or female 18 to 60 years of age
7. Body mass index (BMI) of ≥ 17 kg/m²
8. Non-smoking for a minimum of two years, including cigarettes, cigars, and e-cigarettes
9. Stable pulmonary symptoms associated with CF
10. Creatinine clearance > 60 mL/min, as calculated by Cockcroft-Gault equation based on actual body weight

11. A. Women of childbearing potential must agree to use a highly effective method of birth control (defined as those, alone or in combination, that result in a low failure rate [ie, less than 1% per year]). See Section 6.3.3 for a list of highly effective methods of birth control.
11. B. Men must agree to use barrier contraception (ie, condoms) except when infertility is documented (eg, bilateral orchidectomy or azospermia and/or infertility secondary to CF)
12. FEV₁ ≥ 70% of predicted normal for age, gender, and height (post-bronchodilator value using NHANES III standards) at screening
13. Stable lung function determined by the treating physician, provided FEV₁ at Day -1 is within 10% of FEV₁ at screening.

NOTE: Eligibility criteria 14 through 20 relate to acceptable laboratory values at screening. Subjects with a screening laboratory value outside the specified range may be permitted if the value is not clinically significant in the opinion of the Investigator, with concurrence from the Sponsor's Medical Monitor.

14. Total WBC ≤ 12,000/μL
15. Hemoglobin > 10 g/dL
16. Hematocrit > 30%
17. Platelet count between 150 and 450 x 10³/μL
18. Prothrombin time, international normalized ratio (INR) and partial thromboplastin time within normal limits
19. Serum albumin > 2.5 g/dL at screening
20. Liver function tests within 2X the upper limit of normal (SGPT/ALT, SGOT/AST, GGT, alkaline phosphatase, bilirubin [total and direct])

5.4 Exclusion Criteria

1. Personal or family history of prolonged QT syndrome; or a QTc interval > 430 msec (males) or > 450 msec (females) using Bazett's formula (QTcB)
2. Change in body weight within 90 days prior to Day 1 that is considered clinically significant by the Investigator
3. Abnormal vital signs at screening: heart rate > 120 bpm at rest; systolic blood pressure > 140 or < 90 mmHg; respiration rate > 24 bpm; and SpO₂ < 92% at rest
4. History of alcohol abuse within the past 24 months or positive drug test at screening. Presence of drug(s) administered for known conditions are permitted with concurrence from the Sponsor's Medical Monitor (eg, benzodiazepine, oral cannabis).
5. Any infection including acute upper respiratory or lower respiratory infections, pulmonary exacerbation, changes in therapy for pulmonary disease, or any non

CF-related illness which results in the initiation of any new therapy within 30 days prior to Day 1

6. Clinically significant, abnormal screening laboratory value (as determined by the Investigator) or any abnormal screening laboratory value that would place the subject at undue risk while participating in the study (as determined by the Investigator with concurrence from the Sponsor's Medical Monitor)
7. Breast-feeding or pregnant female
8. Significant change in maintenance medications for CF within 30 days of Day 1
9. Use of lumacaftor or ivacaftor within 45 days of Day 1
10. Use of any investigational drug (other than QR-010) or device within 30 days of Day 1
11. Unable to or unwilling to perform key safety evaluations such as spirometry
12. Unable to participate in standardized airway clearance techniques
13. Presence or medical history of clinically significant disease which precludes study participation or prevents determination of outcome measures
14. History of lung transplantation
15. Hemoptysis of greater than 30 mLs within 90 days prior to Day 1, or hospitalization for hemoptysis within 6 months of Day 1
16. Any severe, acute, or chronic medical or psychiatric condition, laboratory abnormality, or other condition that, in the judgment of the Investigator, would place the subject at undue risk, interfere with the results of the study or make the subject otherwise unsuitable
17. Any difficulty complying with protocol requirements that may increase the risk associated with study participation or study drug administration or may interfere with safety

